4.3 Study Patients

4.3.1 Disposition of Patients

Patient disposition will be summarized for all enrolled patients (i.e., the Intent-to-Treat Analysis Set) by cohort and over all patients combined within each part of the study (Simon 2-Stage, Expansion). Summaries will include the number and percentage of patients in each analysis set, completing the study, and discontinuing the study early by the primary reason for discontinuation.

For the post-Stage 2 expansion phase of the study, disposition will also be summarized for the subgroup of patients in the Intent-to-Treat Analysis Set with second-line EBV⁺ lymphoma as defined in Section 4.1.5.

The number and percentage of screen failures within each part will be presented by screen failure reason, based on the total number of patients screened.

4.3.2 Protocol Deviations

Important Protocol Deviations (IPDs) will be summarized by cohort and over all patients combined for the Intent-to-Treat Analysis Set within each part of the study (Simon 2-Stage, Expansion). Important Protocol Deviations are identified by the Sponsor and are defined in the ICH guideline *Structure and Content of Clinical Study Reports – Questions and Answers (E3[R1], 2013)* as a subset of protocol deviations that might significantly affect the completeness, accuracy, and/or reliability of the study data or that might significantly affect a patient's rights, safety, or well-being.

For the post-Stage 2 expansion phase of the study, disposition will also be summarized for the subgroup of patients in the Intent-to-Treat Analysis Set with second-line EBV⁺ lymphoma as defined in Section 4.1.5. All IPDs will be determined and appropriately categorized prior to database lock. The number and percentage of patients with any IPDs as well as the number and percentage of patients with IPDs within each category will be presented.

4.4 Demographic and Other Baseline Characteristics

Demographic and baseline characteristic variables will be summarized by cohort and over all patients combined within each part of the study (Simon 2-Stage, Expansion) for the Modified Intent-to-Treat, Safety, and Efficacy Evaluable Analysis Sets. Demographic and baseline characteristic variable summaries may also be repeated for the Intent-to-Treat Analysis Set if meaningfully different than the Modified Intent-to-Treat Analysis Set.

For the post-Stage 2 expansion phase of the study, demographic and baseline characteristics will also be summarized in the Modified Intent-to-Treat Analysis Set for the subgroup of patients with second-line EBV⁺ lymphoma as defined in Section 4.1, maintaining the option of repeating summaries of demographics and baseline characteristics for the Intent-to-Treat Analysis Set if meaningfully different than the Modified Intent-to-Treat Analysis Set. This subgroup will also be used for the primary interim analyses.

Demographic variables include age, sex, ethnicity, and race. Age as collected in the EDC will be summarized using descriptive statistics. Sex, ethnicity, and race will be summarized with the number and percentage of patients in each parameter category.

Baseline characteristics include medical history, ECOG performance status, height, weight, and body mass index (BMI), lymphoma subtype by central review, time from initial diagnosis, stage of disease at study entry, presence or absence of bone marrow involvement, number and types of prior systemic therapies (and prior local therapies) for lymphoma, and plasma EBV DNA level. Body mass index will be calculated as: weight (kg) / [height (cm) / 100]².

Height, weight, and BMI at baseline will be summarized using descriptive statistics. ECOG performance status will be summarized with the number and percentage of patients in each category.

Medical history conditions will be mapped to preferred terms and system organ classes using the Medical Dictionary for Regulatory Activities (MedDRA, version 26.0). Frequency counts and percentages to summarize patients reporting abnormal medical history by system organ class will be presented.

For lymphoma medical history, pathological diagnosis, the number of prior systemic therapies, presence or absence of bone marrow involvement, best response achieved with the most recent treatment regimen, stage at study entry, whether or not patient is or refractory to last therapy received prior to entering the study, number of prior autologous or allogeneic stem cell transplants, and whether or not the patient has exhausted all available therapies in the opinion of the investigator will be summarized with the number and percentage of patients in each category. The time since the date of original lymphoma primary diagnosis will be summarized using descriptive statistics. All other lymphoma medical history will be included in patient data listings.

4.5 Efficacy Evaluation

For the Simon 2-stage part of the study, since Cohort 3 (PTCL) patients are initially randomized to monotherapy or combination therapy, their data will be summarized as follows: patients randomized to monotherapy, patients who start on monotherapy and then cross over to combination therapy, and patients randomized to combination therapy.

For the post-Stage 2 expansion part of the study, patients with second-line EBV⁺ lymphoma will also be analyzed separately, and the primary efficacy analyses will be performed in this patient subgroup at the interim analysis (see Section 4.5.6.3 for details of this interim efficacy analysis) and at the final analysis.

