# 4.1. Patient Population

#### 4.1.1. Inclusion Criteria

To be eligible for study participation, patients must meet all the following inclusion criteria:

- 1. Adult patients age ≥18 years or as permitted by applicable local regulations at the time of providing informed consent. Patients must be able to swallow whole tablets.
  - a. For patients with PTLD: Age  $\ge 12$  years and weighing  $\ge 40$  kg.
- 2. Histologically confirmed (by 2016 WHO classification (Swerdlow 2016)) EBV+ lymphoma\* per local laboratory by EBER-ISH (or for PTLD only, by LMP-1 immunohistochemistry) on a representative disease specimen. Any degree of EBER-ISH or LMP-1 positivity is considered to be eligible (ie, there is no cut-off value for % positive cells).
  - \* Tumor cells are EBV+, with the exception of AITL, which is characterized by EBV-negative neoplastic T cells and EBV+ associated B-lineage cells (of immunoblastic/plasmablastic immunophenotype)
  - a. A recent FFPE specimen must be available for retrospective central review of diagnosis. FFPE tissue blocks are preferred; if a tissue block is not available, at least 15 unstained slides or freshly cut serial sections (3–5 μm in thickness), preferably with an accompanying block punch will be accepted. The specifications for the age of the tumor samples are:
    - For patients with ENKTL, AITL, PTLD and HIV-L: preferably ≤1 year old. For tumor specimens >1 year old, please consult the Medical Monitor to discuss eligibility.
    - For patients with all other lymphoma subtypes: preferably ≤6 months old. For tumor specimens >6 months old, please consult the Medical Monitor to discuss eligibility.
- 3. **For patients with EBV**+ **DLBCL, NOS:** Relapsed or refractory disease following 1 or more prior systemic therapy(ies) with curative intent. Patients must have received at least one course of an anti-CD20 immunotherapy such as rituximab, and at least one course of anthracycline-based chemotherapy (unless contraindicated, in which case, an accepted anthracycline-free alternative for DLBCL was given).
- 4. **For patients with ENKTL:** Relapsed or refractory disease following 1 or more prior systemic therapy(ies) with a curative intent. Patients must have failed an asparaginase-containing regimen.
- 5. For patients with PTCL (PTCL, NOS and AITL): Relapsed or refractory disease following 2 or more prior systemic therapy(ies) with a curative intent.

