4.1.5 Standard Calculations

Where appropriate, the calculated study day of each assessment or event will be presented with the assessment or event date on patient data listings, where study day will be determined as:

- The assessment/event date minus the date of first dose of study drug, if the assessment/event date is prior to the date of first dose; and
- The assessment/event date minus the date of first dose of study drug, plus one, if the assessment/event date is on or after the date of first dose.

Other variables requiring calculations will be derived using the following formulas:

- **Days:** A duration between two dates expressed in days will be calculated using the following conventions:
 - Later date earlier date + 1, if the earlier date is on or after the reference date of interest (e.g., date of first dose of study drug); or
 - Later date earlier date, if the earlier date is prior to the reference date of interest.

- **Months:** A duration expressed in months will be calculated by dividing the duration in days by (365.25 / 12).
- Years: A duration expressed in years will be calculated by dividing the duration in days by 365.25.
- **Change from Baseline:** Change from baseline will be calculated as the post baseline value minus the baseline value.
- **Percentage Change from Baseline:** Percentage change from baseline will be calculated as the change from baseline divided by the baseline value, multiplied by 100.
- **Second-Line EBV**⁺ **Lymphoma:** Relapsed or refractory disease following 1 prior systemic therapy (regimen). Inclusion in this subgroup will be determined using data collected for line of therapy on the Anti-Cancer Therapy Regimen eCRF.

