A formal interim analysis will be performed for each post-Stage 2 expanded lymphoma subtype cohort in patients with second-line EBV⁺ lymphoma when a total of 40 second-line EBV⁺ lymphoma patients have been followed for at least 6 months or permanently discontinued study treatment. The rationale for selecting 40 patients at the interim analysis is provided in Table 4 below using the Clopper-Pearson binomial confidence intervals of the proportion (Clopper 1934).

Table 4 Sample Sizes for the Interim and Final Analyses of Patients with Second-Line EBV⁺ Lymphoma

Sample Size	Observed Rate	95% CI	Control Rate
	42.5%	(59%, 27%)	25%
40	52.5%	(68%, 36%)	35%
	65%	(79%, 48%)	45%
	40%	(55%, 26%)	25%
50	50%	(64%, 36%)	35%
	62%	(75%, 47%)	45%
	38%	(52%, 26%)	25%
60	48%	(61%, 35%)	35%

Sample Size	Observed Rate	95% CI	Control Rate
	60%	(72%, 46%)	45%

If the observed effect is 52.5% (i.e., 21 responders out of 40 patients) at the interim analysis, then the 95% CI will exclude an ORR effect size of 35%. For these interim analyses, the observed ORR by IRC will be evaluated along with 95% CI. Other secondary endpoints will be evaluated with descriptive statistics such as both point and interval estimates.

The final efficacy analysis will be performed as planned with total 120 patients in the expansion stage of the study. Approximately 50-60 patients with second-line EBV⁺ lymphoma are anticipated to be enrolled at the time of the final analyses. The final analyses will be performed when all patients, including second-line EBV⁺ lymphoma patients, have been followed for at least 6 months or permanently discontinued study treatment.

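### The second-line primary subgroup (1 prior regimen) and the PTCL entry criterion (at least 2 prior therapies) exclude each other if lines and therapies are counted alike

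*SAP*

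**What the plan says.** **Primary population of the expansion.** SAP 4.5 analyses second-line patients separately in the post-Stage 2 expansion and states that "the primary efficacy analyses will be performed in this patient subgroup at the interim analysis"; the same sentence adds the final analysis. SAP 4.4 repeats this for the interim only: "This subgroup will also be used for the primary interim analyses".

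**Definition of second-line.** SAP 4.1.5: "Relapsed or refractory disease following 1 prior systemic therapy (regimen". On how patients are classified it says: "Inclusion in this subgroup will be determined using data collected for line of therapy on the Anti-Cancer Therapy Regimen eCRF".

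**Interim and final numbers.** SAP 4.7: "A formal interim analysis will be performed for each post-Stage 2 expanded lymphoma subtype cohort in patients with second-line" disease, once 40 such patients have 6 months of follow-up or are permanently off treatment. For the final analysis it projects "Approximately 50-60 patients with second-line" disease among the 120 expansion patients. SAP 4.5.6.3 adds the decision rule: at least 26 responses in the 40 would be declared overwhelming efficacy and could support an accelerated submission.

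**Who can enter.** Protocol 4.1.1, criterion 5 (repeated in the Synopsis), requires for PTCL: "Relapsed or refractory disease following 2 or more prior systemic therapy(ies) with a curative intent". For DLBCL, criterion 3 requires: "Relapsed or refractory disease following 1 or more prior systemic therapy(ies) with curative intent". For PTLD, criterion 7 speaks of at least one prior therapy.

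**Why PTCL matters here.** SAP 4.7 reports a Stage 2 response rate for one cohort only, PTCL at 33.3%, and derives N=120 from that rate.

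**The concern.** The SAP's primary subgroup needs exactly one prior regimen, and the PTCL entry rule needs at least two prior therapies. If both documents count in the same unit, no patient can satisfy both. The cohort used to size the expansion would then have a stated primary analysis that no protocol-eligible patient can enter, and an interim trigger that cannot be reached without protocol deviations.

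At stake for PTCL are the 40-patient interim, the 26-of-40 rule and the second-line thresholds in SAP Table 4. The study is open-label. If the conflict surfaces only after responses have been seen, the replacement primary population would be chosen with the data in view. SAP section 1 says that its descriptions are there to avoid post hoc decisions of that kind.

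**Working it through.** **Inputs.** Minimum prior systemic therapies for PTCL: 2 (Protocol 4.1.1, criterion 5). Prior regimens for second-line: 1 (SAP 4.1.5). Second-line patients needed at the interim: 40 (SAP 4.5.6.3 and 4.7). Second-line patients expected at the final analysis: 50 to 60 of 120 (same sections). PTCL Stage 2 response rate: 33.3% (SAP 4.7). Reference rate for the whole expanded cohort: 25% (Protocol 9.4).

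**Step 1: reproduce the plan's figures.** The exact (Clopper-Pearson) 95% interval for x responders in n has lower limit equal to the 2.5% quantile of Beta(x, n−x+1) and upper limit equal to the 97.5% quantile of Beta(x+1, n−x).

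| n | x | Rate | Exact 95% CI | SAP Table 4 |
|---|---|---|---|---|
| 40 | 17 | 42.5% | 27.0%–59.1% | 27%, 59% |
| 40 | 21 | 52.5% | 36.1%–68.5% | 36%, 68% |
| 40 | 26 | 65.0% | 48.3%–79.4% | 48%, 79% |
| 50 | 20 | 40.0% | 26.4%–54.8% | 26%, 55% |
| 50 | 25 | 50.0% | 35.5%–64.5% | 36%, 64% |
| 50 | 31 | 62.0% | 47.2%–75.4% | 47%, 75% |
| 60 | 23 | 38.3% | 26.1%–51.8% | 26%, 52% |
| 60 | 29 | 48.3% | 35.2%–61.6% | 35%, 61% |
| 60 | 36 | 60.0% | 46.5%–72.4% | 46%, 72% |

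All nine rows agree to within one percentage point. For the expansion size, 40/120 (33.3%) has a lower limit of 24.99%, which matches the SAP's N=120 up to rounding. The interim arithmetic is sound. The question is who can be in the 40.

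**Step 2: compare the two sets.** Let k be the number of prior systemic therapies.
- Protocol-eligible PTCL: k ≥ 2.
- Second-line: k = 1.
- If k is counted the same way in both, the intersection is empty, so 0 of 120 eligible PTCL expansion patients are second-line.

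**Step 3: compare with what the SAP needs.**
- Interim: 40/120 = 33.3% of the expansion; eligible under Step 2: 0.
- Final: 50/120 = 41.7% to 60/120 = 50.0%; eligible under Step 2: 0.

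**Step 4: test the counting condition.** SAP 4.5.6.8 divides the number of prior systemic therapies into one line and two or more lines, so it treats therapies and lines as the same unit. The curative-intent qualifier in criterion 5 does not help, because two curative-intent therapies are still two systemic therapies. One gap remains: two therapies recorded within a single eCRF regimen line. No text defines such a rule and the eCRF is not supplied. If that recording is used, the count could exceed 0, but the documents do not give it.

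**Step 5: could deviators fill the subgroup?** The SAP's modified ITT set (4.2) does not require eligibility, so deviators would stay in. The Efficacy-Evaluable set does require it, and SAP 4.5.6.8 plans second-line summaries in that set too. Under the Step 2 condition it would hold no second-line PTCL patient. Protocol 7.1.8 has the sponsor approve eligibility before enrolment, so 40 deviators cannot be what was planned.

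**Step 6: reference counts for the whole cohort, for information.** Against 25%, the smallest count whose exact lower limit exceeds the reference is 41/120 (34.2%, CI 25.76%–43.38%), since 40/120 gives 24.99%. At n=40 it is 17/40 (lower limit 27.0%), since 16/40 gives 24.9%.

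**The case against.** **The zero is conditional.** Criterion 5 counts therapies and SAP 4.1.5 counts regimens by eCRF line. A reader might infer that the documents prove an empty PTCL subgroup. They do not. They make the common unit likely (SAP 4.5.6.8) but never define it. This stands, and the conclusion carries the condition.

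**The interim is wider than the 40.** SAP 4.5.6.3 also names an interim look at the expanded cohort overall. That is correct, but the 40-patient trigger for the look is defined in second-line patients, so the credit is partial.

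**PTCL is not left without an analysis.** A reader might infer that the PTCL expansion has no usable result. The documents do not support that. SAP 4.1.1 and 4.5.3 report response by cohort with an exact interval, and SAP 3.3.2 keeps a final analysis of the entire cohort. SAP 4.1.1 and 4.5.6.5 make results descriptive, without type I error adjustment, and SAP 4.5.6.3 continues enrolment to 120 whatever the interim shows. All of this stands and limits the damage. None of it gives PTCL a workable primary analysis as SAP 4.5 states it.

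**Could the 40 be pooled across subtypes?** SAP 4.7 says each expanded subtype cohort, and SAP 3.3.2 and 4.5.6.3 lean the same way. A pooled 40 would still contain no eligible PTCL patient under the same condition.

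**How many cohorts does the problem touch?** A reader might take the 360 expansion patients in Protocol 3.1 as three cohorts of 120 and identify them with Cohorts 1, 3b and 5. The same sentence counts 60 = 6 × 10 in Stage 1 and 66 = 6 × 11 in Stage 2, so it includes the closed cohorts, and the inference fails.

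**Is there a route for PTCL after one therapy?** Protocol 1.3.4 mentions one or more prior therapies, but for the study population as a whole. No passage makes an exception to criterion 5.

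**Conclusion.** The texts conflict. SAP 4.5 and 4.7 place the expansion's primary analyses and the 40-patient trigger in patients with one prior regimen, and criterion 5 keeps such patients out of the PTCL cohort. If eCRF lines are counted as criterion 5 counts therapies, eligible second-line PTCL patients number 0, against 40 needed and 50 to 60 expected. The stated PTCL primary subgroup is then empty apart from deviators, and neither the trigger nor the 26/40 rule (65%, exact CI 48.3%–79.4%) can be evaluated for PTCL.

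The loss stops there. The whole-cohort estimate survives; 40/120, for example, would give 33.3% with exact CI 24.99%–42.5%. Cohorts that admit one prior therapy, such as DLBCL and PTLD, are unaffected.

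Confidence is high that the supplied texts conflict, and moderate on the operational consequence. The latter rests on the line-counting condition, and on the supplied protocol being the amendment 5 (19 October 2023) against which SAP 4.8 is written. The protocol records a closure on 17 October 2023, which is compatible with that but does not confirm it. The accelerated-submission rule tied to this subgroup is the main reason to settle the matter before the interim.

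**What to change.** Before the interim, reconcile criterion 5 with SAP 3.3.2, 4.1.5, 4.4, 4.5, 4.5.6.3 and 4.7. Which eligibility rule is right is for the sponsor to decide, not this review.

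- **If criterion 5 stands:** amend the SAP to name the whole expanded PTCL cohort as the primary population and as the interim trigger. Re-derive or drop the 26/40 rule and the Table 4 thresholds for PTCL, because they were set for second-line patients. The sponsor should choose and justify the reference rate; the counts in the working use the protocol's 25% for information only. Cost: an SAP amendment, with the planned 120 patients unchanged.
- **If second-line PTCL is intended:** make the eligibility and SAP passages consistent. Cost: a protocol amendment as well. Expansion patients already enrolled after at least two therapies would not count toward the 40 or the 50 to 60, and the documents do not say how many there are.
- **In either case:** state in SAP 4.1.5 how eCRF lines map to prior systemic therapies. Also list the second-line primary population in SAP 4.8, which now records the change of analysis set and the added endpoints but not this change. Cost: text only.

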4.5.3 Primary Efficacy Endpoint Analysis Methods

The primary efficacy endpoint is ORR assessed by an IRC.

Patients will be analyzed according to their cohort/lymphoma subtype. For Cohort 3a patients who cross over from monotherapy to receive combination therapy, the CT/PET scan immediately preceding their first dose of combination therapy will be used for their baseline tumor assessment (and not the scan performed at the screening visit).

The number and percentage of patients with a CR or PR after initiation of treatment will be summarized by cohort. Ninety-five percent (95%) confidence intervals (CIs) around the ORR (CR + PR) will be calculated using the Clopper-Pearson method. For patients with measurable disease, a swimmer plot of each patient's overall tumor response assessments during study participation and patient deaths (for those patients who have died) will be presented by cohort.

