4.5.6.3 Interim Analyses and Data Monitoring

In addition to the Stage 1 analysis specified by Simon's decision criteria for proceeding to Stage 2, a formal interim analysis will be performed for a post-Stage 2 expanded lymphoma subtype cohort overall and for patients with second-line EBV⁺ lymphoma. A total of 40 second-line EBV⁺ lymphoma patients who have been followed for at least 6 months or permanently discontinued study treatment, will be used for the interim analysis. For these interim analyses, the observed ORR by IRC will be evaluated along with the 95% confidence interval. Other secondary endpoints will be evaluated with descriptive statistics such as both point and interval estimates.

The final efficacy analysis will be performed as planned with a total 120 patients with relapsed or refractory EBV⁺ lymphoma patients enrolled in the post-Stage 2 expansion phase of the study, which are anticipated to include approximately 50-60 patients with second-line EBV⁺ lymphoma. The final analysis will be performed when all patients, including those with second-line EBV⁺ lymphoma have been followed for at least 6 months or permanently discontinued study treatment. If at least 26 responses are observed for an ORR ≥65% (95% CI: 79%, 48%) at interim analysis of 40 patients with second-line EBV⁺ lymphoma, then overwhelming efficacy would be declared to potentially support accelerated NDA submission after these patients are followed for at least 6 months for DOR and other secondary endpoints. This magnitude of treatment effect at the interim analysis would exclude an approximately 47% ORR with 95% confidence. Of note, enrollment into any post-Stage 2 expansion cohort would continue to complete the planned enrollment of 120 patients for the final analysis independent of the interim analysis outcome.

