4.5.6.6 Use of an "Efficacy Subset" of Patients

The primary efficacy analysis will be performed in the Modified Intent-to-Treat Analysis Set; the Intent-to-Treat and Efficacy Evaluable Analysis Sets will be utilized as sensitivity analyses.

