4.5.6.8 Examination of Subgroups

The primary efficacy endpoint may be summarized by various subgroups of interest based on baseline and demographic categories including age (<65 years of age and \ge 65 years of age), ECOG performance status at study entry (0, 1, and 2), number of prior systemic therapies (1 line and 2+ lines), stage of disease at study entry (Stages 1-2 and Stages 3-4), gender, and race. Summaries by subgroup will only be produced if there are at least 6 patients in the category of interest.

For the post-Stage 2 expansion part of the study, all efficacy analyses will also be summarized in the Modified Intent-to-Treat and Efficacy Evaluable Analysis Sets for the subgroup of patients with second-line EBV⁺ lymphoma as defined in Section 4.1.

Additional subgroup analyses may be performed post-hoc, as appropriate.

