4.7 Determination of Sample Size

This multinational, multicenter study will employ a Simon's optimal 2-stage design to allow termination of enrollment into cohorts where treatment appears futile (Simon 1989). The decision to transition from Stage 1 to Stage 2 is dependent on the assumption of ORR: ORR \leq 10% (poor response); ORR \geq 35% (good response). The sample size estimation uses 1-sided alpha = 0.05 and targets statistical power = 85%.

Using the Simon's 2-stage design approach, the null hypothesis that the true response rate is 10% will be tested against a one-sided alternative. In the first stage, up to 10 patients will be accrued in each cohort. If there are 1 or fewer responses, the cohort will

be discontinued. If the cohort fails to enroll any patients within 1 year from the enrollment of the first patient, the cohort will be considered for termination of enrollment. Otherwise, if at least 2 patients in a cohort respond, additional patients will be accrued for a total of 21 in the cohort. The null hypothesis that the true response rate is 10% will be rejected in each cohort where 5 or more responses are observed in 21 patients. This design yields a type I error rate of 0.0440 and power of 86.2% within each cohort where the true response rate is 35%.

If 10 patients of a given lymphoma subtype are enrolled into Cohort 7, then the Simon's decision criteria will be applied to determine whether or not to add patients in Stage 2 for that subtype. If none of the subtypes represented in Cohort 7 enrolls at least 10 patients, efficacy data collected on those patients will be listed, but not summarized by group. All patients will be summarized for safety, regardless of the decision to discontinue enrollment into any cohort.

If at the end of Stage 2 there are at least 7 responders observed in the initial 21 patients in any cohort (ORR \geq 33.3%), enrollment will be expanded to include up to 120 additional patients in that cohort (N=141), with an interim analysis in that cohort to be performed as described in Section 4.5.6.3. Simon's Stage 2 estimate was ORR=33.3% for the PTCL cohort. Using Clopper-Pearson Exact confidence interval approach, the sample size for a 95% CI that would exclude 25% if the ORR was 33.3% was N=120. Using ORR=35%, the minimum sample size is estimated to be N=85.

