4.8 Changes in the Conduct of the Study or Planned Analyses

The following changes were made to planned analyses identified during the development of this SAP, relative to the descriptions provided within the clinical study protocol amendment 5, dated 19 October 2023:

The protocol states that the Intent-to-Treat population will be used for the primary efficacy analysis. This SAP substitutes the following analysis sets as defined in Section 4.2 above for efficacy analyses, preserving the opportunity to repeat efficacy summaries for the Intent-to-Treat Analysis Set if meaningfully different than the Modified Intent-to-Treat Analysis Set:

- Modified Intent-to-Treat Analysis Set
- Efficacy-Evaluable Analysis Set

Addition of the following secondary efficacy endpoints as defined in Section 3.4.1.2 above:

- Complete response rate
- Duration of complete response
- Time to response

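### The SAP does not settle whether the expansion's final primary conclusion rests on about 50–60 second-line patients or on all 120, and N=120 was derived only for the whole cohort

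*SAP*

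**What the plan says.** The relevant statements, all about the post-Stage 2 expansion unless noted:

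- SAP 4.5 on second-line patients: "the primary efficacy analyses will be performed in this patient subgroup at the interim analysis", and the same sentence adds the final analysis.
- SAP 4.5.3 on the primary endpoint in general: "Patients will be analyzed according to their cohort/lymphoma subtype". There is no restriction by line of therapy.
- SAP 4.5.6.3: "The final efficacy analysis will be performed as planned with a total 120 patients", of whom about 50–60 are expected to be second-line. SAP 4.7 repeats this.
- SAP 4.5.6.8, under subgroups: "all efficacy analyses will also be summarized in the Modified Intent-to-Treat and Efficacy Evaluable Analysis Sets for the subgroup of patients with second-line" lymphoma.
- SAP 3.3.2: after a positive interim, the final analysis is still run in all second-line patients and in the entire cohort. Neither is ranked above the other.
- SAP 4.7, on the size of the expansion: "the sample size for a 95% CI that would exclude 25% if the ORR was 33.3% was N=120". It adds N=85 if the ORR is 35%.
- SAP 4.7, Table 4: precision at n=40, 50 and 60 second-line patients against control rates of 25%, 35% and 45%.

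The protocol (9.4, 9.6.1, 9.8) works by cohort and defines no second-line analysis population. SAP 4.8 opens with "The following changes were made to planned analyses identified during the development of this SAP". It lists the change of analysis set and three added endpoints, but nothing about second-line patients.

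**The concern.** A single-arm expansion needs one population whose interval is read as the answer. Here one section puts the primary analyses in a subgroup of roughly half the patients, while the sections on final analysis and sample size describe the whole cohort. Because both analyses will be produced, and in 3.3.2 neither outranks the other, the sponsor could lead with either result after seeing open-label data. SAP 4.5.6.3 contemplates that expansion results may support an NDA submission, so the choice has consequences.

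The sizing is tied to the same question. If second-line is the primary population, the stated derivation of N=120 does not describe the precision of the primary result. No control rate is fixed against which that result would be read at the final analysis.

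**Working it through.** **Inputs.** Clopper-Pearson two-sided 95% interval (SAP 4.5.3); N=120 at ORR 33.3% and N=85 at 35%, both excluding 25% (SAP 4.7); 50–60 second-line patients among 120 (SAP 4.5.6.3). Assumptions not in the documents: the true ORR in each line-of-therapy group, and 25% as the benchmark for second-line patients as well as for the cohort.

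**Step 1: reproduce the SAP's figures.** The lower limit for x responders in n is the 2.5% quantile of Beta(x, n−x+1). For 40/120 the interval is 24.99% to 42.5%. Allowing fractional responders, the smallest n whose lower limit exceeds 25% is 121 at 33.3% and 86 at 35%. The SAP's 120 and 85 are therefore reproduced to within a patient or two. Strictly, 40/120 just fails and 41 responders are needed. The Table 4 rows checked also reproduce: 20/50 gives 26.4–54.8%, 23/60 gives 26.1–51.8%, and 26/40 gives 48.3–79.4%.

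**Step 2: chance of excluding 25%.** Let c be the smallest count whose lower limit exceeds 25%. The chance is P(Bin(n, p) ≥ c).

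| n | c | observed rate | lower limit | chance at p=33.3% | chance at p=35% |
|---|---|---|---|---|---|
| 50 | 20 | 40.0% | 26.4% | 19.6% | 27.4% |
| 55 | 21 | 38.2% | 25.4% | 26.5% | 35.7% |
| 60 | 23 | 38.3% | 26.1% | 24.4% | 33.8% |
| 120 | 41 | 34.2% | 25.8% | 45.7% | 61.0% |

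Applying the SAP's own sizing rule to second-line patients would take about 120 of them, which is 120 × 120/60 = 240 to 120 × 120/50 = 288 patients in all.

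**Step 3: how often the two populations disagree.** Take X ~ Bin(m, p₁) for the m second-line patients and Y ~ Bin(120−m, p₂) for the rest. Disagreement = P(X ≥ c, X+Y ≤ 40) + P(X < c, X+Y ≥ 41), computed exactly.

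| true ORR, second-line / later-line | m=50 | m=55 | m=60 |
|---|---|---|---|
| 25% / 25% | 2.2% | 2.6% | 2.1% |
| 30% / 30% | 15.9% | 15.6% | 14.8% |
| 33.3% / 33.3% | 32.2% | 28.7% | 28.5% |
| 35% / 35% | 38.7% | 33.0% | 33.2% |
| 40% / 40% | 38.0% | 28.4% | 28.6% |
| 45% / 45% | 19.2% | 12.0% | 11.6% |
| 50% / 50% | 5.9% | 2.9% | 2.6% |
| 45% / 25% | 37.9% | 35.8% | 28.9% |
| 40% / 30% | 26.3% | 25.0% | 22.7% |
| 30% / 40% | 60.0% | 53.3% | 51.1% |

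**Step 4: direction.** At a common 33.3–35%, the cohort alone excludes 25% in 24–36% of trials and second-line alone in 3–5%. With 45% / 25% this reverses: second-line alone 28–36%, cohort alone 1–2%. That scenario fits the sizing, because the cohort average is (50×45% + 70×25%)/120 = 33.3% for m=50 and (60×45% + 60×25%)/120 = 35% for m=60.

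**The case against.** Several defences have substance.

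- **A reader might infer that the SAP names two rival primary populations.** It does not. Only 4.5 attaches the word primary to a line-of-therapy group. Sections 4.5.6.3 and 4.7 speak of the final efficacy analysis, which can be read as fixing its timing and total size. The statement in 4.5.6.6 that "The primary efficacy analysis will be performed in the Modified Intent-to-Treat Analysis Set" names an analysis set, and 4.5.6.8 applies that set within second-line patients, so it is compatible with 4.5. What remains is a conflict with the cohort-level analysis in 4.5.3 and a missing rank order.
- **Second-line is not without a sizing rationale.** Table 4 covers the final as well as the interim analysis, and its 25% rows (40% at n=50, 38% at n=60) match the thresholds in Step 2. This stands. The table still offers three control rates and selects none for the final analysis.
- **A reader might take one-in-three disagreement as a property of the design.** It is not. It needs equal rates near 33–40% and a 25% second-line benchmark that the SAP never sets.
- **A reader might infer that the move to second-line was driven by the Stage 2 result, since 4.7 cites 33.3% for PTCL.** The documents do not show this. Stage 2 must be known before any expansion, the 120 are additional patients, the two parts are analysed separately (SAP 4.1.1), and the SAP is to be final before any formal interim or final analysis (SAP 1).
- **The results are called descriptive, with no hypothesis test (SAP 4.5.6.5).** That removes a formal type I error claim. It does not remove the need to say in advance which interval is the primary one, given the declaration of overwhelming efficacy envisaged in 4.5.6.3.

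**Conclusion.** The point holds as a contradiction about rank: the SAP does not say consistently which population carries the expansion's final primary conclusion, and the departure from the protocol's cohort-level primary is undeclared. That finding rests on the text alone.

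The numbers show that the choice can matter, under stated assumptions. With one true ORR of 33.3–35% for everyone and 25% as the benchmark for both, all 120 exclude 25% with probability 46–61% and 50–60 second-line patients with probability 20–36%; the conclusions differ in 28–39% of trials. Disagreement drops to about 2% at a common 25% and to 3–6% at 50%, and exceeds 50% in the 30% / 40% scenario. Neither population is the safer choice in general: the cohort is favoured if rates are equal, second-line if its patients respond much better.

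A related conflict bears on the same subgroup. SAP 4.1.5 defines second-line as disease after one prior systemic therapy, while protocol 4.1.1, inclusion criterion 5, requires two or more for PTCL. As the supplied texts stand, the one cohort whose Stage 2 estimate is cited could not supply the second-line patients.

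**What to change.** Before any expansion efficacy data are reviewed:

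1. State the same single primary population and a single benchmark for the final analysis in SAP 4.5, 4.5.6.3 and 4.7, and label the other population secondary. Align 3.3.2 and 4.5.6.8 with this.
2. Choose openly. All 120 against 25% is the option that matches the stated N=120. If second-line stays primary, 4.7 should name its control rate and say that N=120 was not sized for it. A formal testing order between the two is optional, as no tests are planned.
3. Record the change from the protocol in 4.8.
4. Reconcile the SAP's second-line definition with the protocol's PTCL entry criterion.

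Items 1 to 3 cost SAP wording only. Item 4 may reach the protocol, depending on how it is resolved. The real price is that the sponsor gives up the freedom to lead with whichever population looks better.
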